6.3 Excluded Medications and Treatments

6.3.1 Excluded Medications

Subjects may not use systemic corticosteroids during four weeks from the day of the treatment (surgery). Representative systemic corticosteroids listed in the ADA/PDR Guide to Dental Therapeutics 5th Edition ⁽⁸⁾ are: hydrocortisone, fludrocortisone, methylprednisolone, prednisolone, prednisone, betamethasone and dexamethasone.

Corticosteroids may disturb the wound healing due to the inhibitory effect on cell proliferation and immune response to infection and therefore, effect the evaluation of effectiveness of GFeBGS.

Also, subjects may not be treated with intravenous bisphosphonates during the study period. The Food and Drug Administration and Novartis Pharmaceuticals Corporation have each issued a drug precaution to health professionals regarding a condition known as Osteonecrosis of the Jaw (ONJ). This condition has been observed in cancer patients who undergo invasive dental procedures such as dental implants or tooth extractions while receiving treatment with intravenous bisphosphonates. The American Association of Periodontology suggests that invasive dental procedures should be avoided unless absolutely necessary in patients who are receiving intravenous bisphosphonates therapy. Two intravenous bisphosphonates are marketed by Novartis under the trade names *Aredia* and *Zometa*. *Bonefos* is another brand of intravenous bisphosphonates marketed by Schering AG.

Other medications which the patient has already been taking as a treatment of periodontitis before enrollment into the study may be continued during the study period as long as the medications remain necessary. Also subjects may take new medications during the study whenever the Investigator decides that the medications are necessary to treat a condition that would otherwise be a contraindication and/or to treat adverse events. Medications other than systemic corticosteroids have little impact on the evaluation of effectiveness of GFeBGS.

Non-steroidal anti-inflammatory drugs (NSAIDs) also will not be allowed to treat post-surgical conditions such as pain because they may affect wound healing and tissue regeneration through the

anti-inflammatory effect. However, acetaminophen products (prescription or over-the-counter) are allowed because the mechanism of pain relief is not mediated by anti-inflammatory effect.

Subjects must be instructed not to take any medications, including over-the-counter products, without first consulting with the Investigator.

6.3.2 Excluded Treatment

Temporary splints may not be used on the study tooth unless the subject already has used the splint before study participation.

The study-treated tooth will not receive any surgical treatments besides the study treatment from the day of the treatment (surgery) until the study ends. Also, no surgical treatments involving implantation of biologic bone grafting material will be allowed in teeth adjacent to the study-treated tooth for the duration of the study. Additionally, no bone grafting materials may be implanted on adjacent teeth in the interproximal space. Surgical treatments at the adjacent teeth and/or the study-treated tooth may disturb the wound healing, and have an impact on the evaluation of effectiveness and safety of GFeBGS.

However, scaling and root planing will be allowed in teeth adjacent to the study-treated site as these procedures are expected to have little impact on the evaluation of safety and effectiveness of GFeBGS.

6.4 Criteria of Failures (Discontinuation or Withdrawal of a Subject)

The primary reason for discontinuation or withdrawal of the subject from the study should be recorded on the Subject Discontinuation/Withdrawal form (CRF 10) using the following categories:

1. Pre-treatment event or adverse event (AE). The subject has experienced a pre-treatment event or AE that requires early termination because continued participation imposes an unacceptable risk to the subject's health or the subject is unwilling to continue because of the pre-treatment event or AE.
2. Major protocol deviation. The discovery post-randomization that the subject failed to meet protocol entry criteria or did not adhere to protocol requirements, and that continued participation would pose an unacceptable risk to the subject's health.
3. Lost to follow-up. The subject did not return to the clinic and attempts to contact the subject were unsuccessful. Attempts to contact the subject must be documented.
4. Voluntary withdrawal. The subject (or subject's legally acceptable representative) wishes to withdraw from the study. The reason for withdrawal, if provided, should be recorded in the CRF.

Note: All attempts should be made to determine the underlying reason for the withdrawal and, where possible, the primary underlying reason should be recorded (i.e. withdrawal due to an AE should not be recorded in the “voluntary withdrawal” category).

5. Study termination. The Sponsor, IRB or regulatory agency terminates the study.
6. Subject does not meet eligibility requirements at Visit 5 and has not signed the informed consent for enrollment in the study.
7. Unexpected surgery is required including rescue treatment of the target tooth.
8. Excluded medication is required including rescue treatment of the target tooth.
9. Unexpected amount of loss of the device from the target tooth.
10. Unacceptable safety risk develops.
11. Other. Note: The specific reasons should be recorded in the “specify” field of the CRF.

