6.5 Procedures for Discontinuation or Withdrawal of a Subject

The Investigator may terminate a subject’s study participation at any time during the study when the subject meets the study termination criteria described in Section 6.4. In addition, a subject may discontinue his or her participation without giving a reason at any time during the study. Should a subject’s participation be discontinued, the primary criterion for termination must be recorded. In addition, efforts should be made to perform all procedures scheduled for the Early Termination Visit. If a subject is discontinued or withdrawn due to an adverse event, the Sponsor should be notified immediately.

Efforts will be made to avoid any subjects being lost to follow-up during the conduct of the study. Before subjects are considered lost to follow-up, a minimum of 2 documented telephone contact attempts and 1 certified letter within 6 weeks of the most recent planned study visit must be sent in an effort to contact subjects.

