10.3 Subjects Lost-to-Follow-Up

A subject will be considered lost-to-follow-up from the last missed clinical evaluation if all reasonable efforts made to contact the subject and request his/her continued participation in the study have failed. Telephone and written attempts will be made to locate and return such individuals to care. At least two certified letters must be sent. In instances where the individual cannot be located or traced, the circumstances leading to lost-to-follow-up status will be documented. All attempts to contact the subject will be documented. When all attempts have failed and a subject is lost-to-follow-up, a Subject Discontinuation/Withdrawal form (CRF 10) must be completed.

Study ID numbers assigned to subjects who are discontinued will not be reassigned to newly enrolled subjects. Whenever possible, subjects who have been discontinued for reasons other than

lost-to-follow-up will be contacted and requested to participate in ongoing safety data assessments conducted by phone.

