12.1.5 Patient and Visit Deviations

Patients will be evaluated to assess eligibility, treatment compliance, visit compliance, and other protocol deviations such as excessive smoking, poor dental care, concurrent medical conditions impacting effectiveness or safety evaluations, and missed visits. Any post-baseline visits occurring more than two weeks outside of study visit windows will be reported. Withdrawals due to lack of effectiveness or adverse events will also be reported as well as the timing of such events. Dropouts will also be reported as well as the nature and timing of such dropouts for any reason. A 15% allowance has been made for dropouts; treatment assignments for dropouts will not be recycled. All patients will be included in all analyses to the fullest extent possible; no data will be carried forward.

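### Sections 6.4 and 6.5 permit follow-up to end for device loss or a required excluded drug, without a safety condition, so six-month outcomes can go uncollected after a one-time implant

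*Protocol*

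**What the plan says.** Section 6.4 lists eleven categories for discontinuing or withdrawing a subject. Item 8 is "Excluded medication is required including rescue treatment of the target tooth". Item 9 is "Unexpected amount of loss of the device from the target tooth", with no threshold given for the amount. Safety is covered elsewhere in the list: item 1 (adverse events), item 2 (deviations, only where continuing would put the subject's health at unacceptable risk) and item 10, "Unacceptable safety risk develops".

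Section 6.5 gives the list its effect: "The Investigator may terminate a subject’s study participation at any time during the study when the subject meets the study termination criteria". For a discontinued subject, "efforts should be made to perform all procedures scheduled for the Early Termination Visit". Section 10.3 adds that subjects discontinued for reasons other than loss to follow-up will, where possible, be asked to "participate in ongoing safety data assessments conducted by phone".

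On analysis, Section 12.1.5 says "All patients will be included in all analyses to the fullest extent possible; no data will be carried forward". Section 12.1.7 bases the primary analysis on available data without imputation. It adds three sensitivity analyses that score missing outcomes as success or failure.

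**The concern.** In a trial of repeated dosing, a discontinuation rule may serve to stop exposure. Here the graft is placed at Visit 5 and Sections 8.3.5 and 8.3.6 bar further implantation, so no study treatment remains to be stopped. Ending participation under item 8 or 9 only ends observation.

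Both events arise after randomisation. Loss of graft may depend on the material or dose and plausibly goes with poor bone gain. The need for an excluded drug, such as a systemic corticosteroid or an NSAID after surgery, may depend on how the site heals. If such subjects leave before month six, the observed-data comparison is made in a group selected by what happened after randomisation.

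The composite compared across arms also drives dose selection under Section 12.1.10. At about 20 evaluable subjects per arm, each subject is worth 1/20 = 5 percentage points. A later analysis plan cannot restore a radiograph that was never taken. Whether these subjects return for Visits 8 and 9 is a matter of conduct that the protocol has to settle.

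**Working it through.** **1. What happens to a subject under item 8 or 9.**
- Trigger: item 8 or 9, with no safety condition (Section 6.4).
- Consequence: the Investigator may end participation (Section 6.5).
- What is left: one attempted Early Termination Visit (Sections 6.5 and 8.3.6) and safety phone contact (Section 10.3). No text asks for a month-six visit after discontinuation.
- What the endpoint needs: change in attachment level and LBG at six months (Section 4.2.1).
- Can an early value stand in? Section 10.2 codes an out-of-window visit to the closest window, so a late termination visit can supply a six-month value. An early one cannot, and Section 12.1.5 rules out carrying data forward.
- Result: the subject is missing from the primary analysis. The title of Section 6.4 calls these criteria of failures, but nothing in Section 12 scores such subjects as failures in the primary analysis.

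**2. The plan's own figures.** Inputs from Section 12.1.2: LBG difference 1.70 mm, SDs 1.20 and 2.30 mm, 20 per group, two-sided 5%, unequal-variance t-test.
- Standard error = √(1.20²/20 + 2.30²/20) = √(0.0720 + 0.2645) = 0.580.
- Noncentrality = 1.70/0.580 = 2.93, with 28.6 Satterthwaite degrees of freedom.
- Power = 80.8%, which agrees with the stated minimum of 80%.
- Dropout: 94 × 0.85 = 79.9, in line with 80 evaluable subjects. The allowance is 94 − 80 = 14.

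At smaller evaluable numbers the same formula gives 78.6% (19 per group), 76.3% (18) and 70.8% (16). There is little slack below 20.

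**3. Effect on the composite (assumed rates).** The documents give neither a success rate nor a rate of device loss.
- One arm: 94/4 = 23.5, so take 23. Suppose 12 succeed and 2 of the failures are withdrawn. True rate 12/23 = 52.2%; observed rate 12/21 = 57.1%; overstatement 4.9 points.
- General form: if a share f is withdrawn, all of them failures, and a share p of those retained succeed, the whole-arm rate is p(1 − f) and the overstatement is p × f. For f from 5% to 15%, that is 2 to 6 points at p = 40% and 3 to 9 points at p = 60%.
- Unequal withdrawal: 5% on control (p = 40%) and 15% on an active dose (p = 60%). Observed difference: 60 − 40 = 20 points. Counting the withdrawn as failures: 60 × 0.85 − 40 × 0.95 = 51 − 38 = 13 points.

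**4. What the sensitivity analyses recover.** In the first example, scoring missing as failure returns 12/23. That works for a success/failure outcome. LBG is continuous, and the three scoring rules in Section 12.1.7 do not apply to it.

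**The case against.** The strongest reply is that the text requires nothing. Section 6.4 opens as a list of categories for recording the main reason for withdrawal, and Section 6.5 is permissive. An Investigator may keep a subject with graft loss through Visit 9. This stands: a reader might infer that these subjects must be withdrawn and their outcomes thrown away, and the documents do not say so. The weakness is that participation may end, at individual discretion and without a threshold, for reasons tied to outcome.

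A reader might also infer that any post-operative NSAID triggers withdrawal. Item 8 speaks of an excluded medication being required, and a drug the subject takes unprompted fits better under the deviation wording of item 2. An estimate in which drug use consumes the whole allowance of 14 therefore has no support. Nor is item 8 wholly unconnected with safety, since Section 6.3.1 gives a safety reason for excluding intravenous bisphosphonates. The accurate statement is that items 8 and 9 are not conditioned on safety.

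Third, some data may survive. The Early Termination Visit includes the probing and the standardised radiograph, and a late one can count for month six. Section 12.1.7 also compares missingness between arms, reviews reasons for withdrawal, and includes missing-as-failure and worst-case analyses. For the composite these bound the problem well. They are secondary to an observed-data primary analysis, and they do not reach LBG.

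Finally, this is a feasibility study with no labelling use, and the sponsor may choose any dose. That limits the stakes, but the protocol still bases dose selection on the composite.

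**Conclusion.** The point holds as a permissive rule with an avoidable cost. Sections 6.4 and 6.5 allow participation to end for a required excluded medication or for device loss, with no safety condition and no study treatment left to stop. Unless withdrawal falls near month six, the attachment level and radiograph that define the primary endpoint are not collected. The subject then drops out of a primary analysis that makes no imputation. This sits poorly with the aim in Section 12.1.5 of including all patients as fully as possible.

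The size is unknown. The illustrations (about 5 points in one arm from two omitted failures; a 20-point difference shrinking to 13) rest on assumed success and withdrawal rates and on every withdrawn subject being a failure. The direction of bias between arms depends on which arm loses more such subjects, which the documents do not indicate. They do not support the conclusion that outcomes will be lost in every such case.

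**What to change.** In Sections 6.4 and 6.5, record items 8 and 9 as events or protocol deviations. State that an implanted subject who meets only item 8 or 9, without rescue of the tooth, continues the probing and standardised radiograph already scheduled at Visits 8 and 9, unless consent is withdrawn or a safety item (1, 2 or 10) applies. Include these data in the ITT analysis. Decisions on medication, rescue and clinical care stay as they are.

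Reconcile the title of Section 6.4 with Sections 12.1.5 and 12.1.7, which do not count such subjects as failures in the primary analysis.

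The cost is a few sentences, with no new visits or procedures. The small downside is that some subjects with off-protocol medication or graft loss remain in the ITT data. If a view without them is wanted, it needs its own definition, because the mITT set in Section 12.1.3 names neither event.

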6.5 Procedures for Discontinuation or Withdrawal of a Subject

The Investigator may terminate a subject’s study participation at any time during the study when the subject meets the study termination criteria described in Section 6.4. In addition, a subject may discontinue his or her participation without giving a reason at any time during the study. Should a subject’s participation be discontinued, the primary criterion for termination must be recorded. In addition, efforts should be made to perform all procedures scheduled for the Early Termination Visit. If a subject is discontinued or withdrawn due to an adverse event, the Sponsor should be notified immediately.

Efforts will be made to avoid any subjects being lost to follow-up during the conduct of the study. Before subjects are considered lost to follow-up, a minimum of 2 documented telephone contact attempts and 1 certified letter within 6 weeks of the most recent planned study visit must be sent in an effort to contact subjects.

7.0 INVESTIGATIONAL DEVICE DESCRIPTION

7.1 Investigational Device

7.1.1 Manufacturing, Packaging, and Labeling

7.1.1.1 Description of Investigational Device

1. Components

The investigational device, [REDACTED] GFeBGS, is supplied in a kit which consists of three components and one accessory:

- 1 each sterile β -TCP in a portion cup
- 1 each vial that contains a sterile lyophilized cake with rh-bFGF.
- 1 each sterile HPC solution in a syringe
- 1 each 18G blunt needle

2. Product code: [REDACTED]

3. Generic name:

rh-bFGF: trafermin (genetic recombinant)
 β - TCP: β - tricalcium phosphate

4. Molecular formula:

rh-bFGF: $C_{764}H_{1201}N_{217}O_{219}S_6$ (Protein composed of 154 amino acids) or
 $C_{761}H_{1196}N_{216}O_{218}S_6$ (Protein composed of 153 amino acids)
 β - TCP: $Ca_3(PO_4)_2$

5. Molecular weight:

rh-bFGF: 17,122.67 (Protein composed of 154 amino acids) or
17,051.59 (Protein composed of 153 amino acids)
 β - TCP: 310.18

6. Content of active ingredients

- Treatment I: β -TCP with 0.5 mg trafermin-containing lyophilized rh-FGF (final conc. 0.1%)
- Treatment II: β -TCP with 1.5 mg trafermin-containing lyophilized rh-FGF (final conc. 0.3%)
- Treatment III: β -TCP with 2.0 mg trafermin-containing lyophilized rh-FGF (final conc. 0.4%)

CONFIDENTIAL

- Treatment IV: β -TCP with lyophilized vial (Active control)

7.1.1.2 Investigational Device Preparation Procedure

A copy of the Instructions for Use is provided in Appendix E.

7.1.1.3 Contents of Carton

The investigational and active control devices are packaged identically. The kit components are sterile. The kit is non-sterile.

- 1 sterile vial containing lyophilized cake with or without the Growth Factor (rh-bFGF)
- 1 sterile cup containing 0.5 cc of β -TCP granules
- 1 sterile syringe containing 0.5 ml of 1% HPC solution
- 1 sterile 18G blunt needle

Storage condition: 2-8°C, in a dry place. Do not freeze.

7.1.2 Storage

All investigational devices must be kept in an appropriate, limited-access, secure place until implanted in a study subject or returned to the Sponsor or designee for destruction. All investigational devices must be stored under the conditions specified on the label, and remain in the original container until dispensed. The temperature of the device storage area must be maintained at 2-8°C (36-46°F). The investigational device should not be frozen. The temperature of the device storage area must be logged daily.

Investigational devices should not be used after the expiration date unless subsequent extensions are confirmed by the Sponsor.

Once the β -TCP granules and the rh-bFGF solution are mixed, it should be applied to the surgical site within 5 minutes. Otherwise, it should not be used and should be destroyed following the instructions provided in the Instructions for Use. Note that the product disposition must be designated as destroyed in the Inventory Accountability Log.

7.2 Randomization Code Creation and Storage

The investigational device kits are assembled by a clinical supplies vendor [REDACTED] [REDACTED] and are visually identical. The randomization code will be created by [REDACTED] as the Sponsor's designee. Block randomization will be stratified by smoking status (non-smoker or smoker). The randomization schedule will be provided to the Investigator as a list of sequential product numbers on the label of the carton box

assigned by [REDACTED]. In the event that devices must be disposed of, replacement devices will be made available.

7.3 Investigational Device Blind Maintenance

Each carton box has a label with a scratch off seal masking the identity of the study treatment contained in the box. The seal is not to be scratched off except in the case of an emergency. During regularly scheduled monitoring visits, a study monitor will perform an inventory of investigational device kits and verify that none of the seals have been scratched off.

All unassigned kits will be counted and returned to [REDACTED] before study closure. All of used kit package containing the empty container of each component also will be returned to [REDACTED] before study closure.

7.4 Unblinding Procedure

The blinded information can be revealed in emergency situations only. In such an emergency, the Primary Investigator at the investigational site will break the blind information for only the subject involved by scratching off the seal on that subject's box. The Primary Investigator is instructed to notify the Sponsor immediately in case of such an emergency.

7.5 Accountability and Return of Investigational Device

Upon receipt of investigational device kit delivered by [REDACTED], the Investigator or designee must verify the contents of the shipments against the packing list. The verifier should ensure that the quantity received matches the quantity listed as shipped on the packing list, the investigational device kits are received within the labeled storage conditions, and are in good condition. If quantity and conditions are acceptable, the Investigator should acknowledge the receipt of the shipment to [REDACTED] according to the instructions provided by [REDACTED]. If there are any discrepancies between the packing list versus the actual product received, [REDACTED] must be contacted to resolve the issue. The Investigator or designee must maintain 100% accountability for investigational device kits received and dispensed during his or her entire participation in the study. If any dispensing errors or discrepancies are discovered, the Sponsor must be notified immediately.

The Investigator or designee must record the current inventory of the investigational device kits on a Device Inventory Log. The following information will be recorded at a minimum: protocol number and title, name of Investigator, investigational site, product number, including the initials of the person receiving the investigational device kit. The log should include all required information as a separate entry for each subject who is implanted with the contents of the investigational device kit.

Before the investigational device kits are returned to [REDACTED] and at appropriate intervals, a clinical monitor will perform the investigational device kits accountability and reconciliation process. The Investigator will retain a copy of the documentation regarding the investigational device kits

accountability including return, and/or destruction of the kits, and originals will be sent to █
█.

